## **Funder**

This project is funded by the Helix Centre and NIHR Imperial Biomedical Research Council

This protocol describes a feasibility study for the OnTrack intervention and provides information about procedures for entering participants. Every care was taken in its drafting, but corrections or amendments may be necessary. These will be circulated to investigators in the study. Problems relating to this study should be referred, in the first instance, to the Chief Investigator.

This study will adhere to the principles outlined in the NHS Research Governance Framework for Health and Social Care (2nd edition). It will be conducted in compliance with the protocol, the Data Protection Act and other regulatory requirements as appropriate.

## KEYWORDS

Stroke, Upper Limb Rehabilitation, Sensors, Behaviour

## STUDY SUMMARY

**TITLE** Feasibility study of OnTrack - a digital system for upper limb rehabilitation after stroke

**DESIGN & METHODS** Mixed methods

**AIMS** Assess the feasibility of 'OnTrack' (a new arm rehabilitation system), for use by patients, and frontline staff in stroke rehabilitation services.

**OUTCOME** Various. (Including but not exclusive to: interviews; focus groups; **MEASURES** usability questionnaires e.g. system usability scale; functional outcome measures e.g Fugl-Meyer; self-reported outcome measures e.g Motor Activity Log; motivational outcome measures e.g. Patient Activation Measure; and others such as e.g. Friends & Family Test, EQ-5D-5L, Modified Rankin Scale, Montreal Cognitive Assessment, etc.)

**POPULATION** Stroke survivors, their family/carers, clinicians, professionals and lay people working with stroke survivors.

**ELIGIBILITY** Participants will be stroke survivors, relatives/carers of stroke survivors, frontline healthcare workers who treat stroke survivors, managers responsible for stroke service provision and lay people with an involvement in stroke care/delivery.

Participants will be over 18.

**DURATION** 1- 2 years

# 1. INTRODUCTION

## 1.1. BACKGROUND

There are over 100,000 strokes per year in the UK, and nearly 1.2 million stroke survivors, of these 25% occur in people under 65 years of age. Stroke is the leading cause of disability in the UK, and almost two thirds of stroke survivors leave hospital with a disability. Upper-limb weakness is the main cause of impairment, and significantly contributes to the loss of independence and isolation stroke survivors feel. Stroke is estimated to cost the NHS and social care in England as much as £1.7 billion per year (Stroke Association, 2017).

Repetitive rehabilitation techniques are widely accepted as the 'gold-standard' for regaining ability after stroke (Kwakkel, 2004). Nonetheless, studies suggest that the actual time patients spend exercising is minimal (Kunkel, 2014). Many current approaches to solving this problem focus on improving the prescribed rehabilitation sessions, often employing gamification techniques (Laver, 2017 and Loureiro, 2011). Whilst this is important, there is untapped potential to increase repetitive rehabilitation by targeting the 90% of the day where patients are going about life's daily activities.

## 1.2 RATIONALE FOR CURRENT STUDY

During the ULRAS ethnographic study we identified that patients struggle to see and keep track of improvements, this impacts their motivation and leaves them dependent on a therapist for feedback. Patient often reported they felt unsupported after leaving hospital and didn't know how to best help themselves improve their arm function. The feedback gathered from patients and clinicians during the ULRAS study was the basis for developing the OnTrack intervention.

OnTrack is a rehabilitation system that uses smart-devices to track arm movement through accelerometry. It combines principles of behaviour change with data on arm movement to provide actionable insights and motivate individuals to increase their arm activity. OnTrack therapists provide regular follow-up consultations to support individuals.

A proof-of-concept has been developed and tested with 10 individuals. A 20% mean increase of activity was observed, with one participant achieving 55% over seven weeks. Participants reported that after using OnTrack they were more aware of their impaired arm and had increased confidence in using it for new tasks.

The proof-of-concept has been developed further through a process co-design with users; therapists and stroke survivor feedback has continued to be incorporated to define the intervention.

OnTrack has the potential to be a scalable solution requiring minimal training that could be used in conjunction with NHS services to help increase the overall amount of arm rehabilitation received.

A study to assess the feasibility of conducting a definitive randomised trial of the OnTrack rehabilitation system is now warranted.

# 2. STUDY OBJECTIVES

Objective 1: To assess the feasibility of the study design and procedures

Objective 2. To explore implementation fidelity and acceptability of OnTrack

The feasibility study will enable the design of a definitive randomised controlled trial testing the effectiveness of OnTrack.

### **3. STUDY DESIGN**

#### **Feasibility study of OnTrack**

A 12-15 month study to assess the feasibility of conducting a definitive randomised trial of the OnTrack rehabilitation system.

#### **Study Design**

A feasibility study and nested process evaluation. The study will be non-randomised; this is a pragmatic solution to set-up, recruitment and delivery across one site within the specified timeframe. The purpose of the study is not to measure clinical effectiveness of the intervention, this will be addressed in a future study if the system proves to be clinically feasible. The design of the study was developed through a collaborative approach between the study researchers, patients, front-line therapists, and the NIHR RDS.

A process evaluation will be completed in parallel to learn about usage and engagement mechanisms of participants, therapists and other frontline staff, providing critical information for implementation fidelity and impact mechanisms necessary for scale-up.

#### **Outcomes**

Feasibility outcomes including the percentage of patients eligible, recruited and completing the 14-week intervention.

Clinical outcomes (such as Fugl-Meyer, Motor Activity Log, Patient Activation Measure, EQ-5D-5L, Friends & Family test, Montreal Cognitive Assessment, Visual Analog Scale Pain, Rankin Scale, etc.) will be collected to identify an appropriate primary outcome, and to estimate parameters for a sample size calculation.

#### **Feasibility assessment criteria:**

1.  $\geq 50\%$  recruitment rate of eligible population
2.  $\geq 50\%$  adherence
3.  $\geq 80\%$  usability, measured by the System Usability Scale (SUS)
4.  $\geq 80\%$  implementation fidelity of OnTrack
5. Sample size estimate for a definitive RCT
6. Indication of the best way to integrate OnTrack into the current rehabilitation environment

#### **Intervention**

The OnTrack system consists of smart-devices (smartphone and smartwatch) and therapist support. Smart-devices are used to track arm movement, receive motivational messages and provide a real-time display of completed arm activity. Therapist support is provided through fortnightly consultations. Additionally, OnTrack helps therapists understand more about how and when patients use their affected arm between treatments.

## **Recruitment**

Therapists will be responsible for identifying suitable patients. They will introduce the study to potential participants and provide information documents. Therapist will allow enough time (minimum 24 hours) for potential participants to think about the pros and cons of participating and to formulate questions. Therapists will be able to answer questions or will liaise with the research team to provide an answer. Once all questions are answered and a potential participant is happy to participate, consent will be taken by the therapist. Only at this stage will limited patient information be shared with the research team. There may be situations where a therapist is only able to take verbal consent from a participant due to time or material constraints, in such cases the researchers will be able to take written consent from the participant upon first meeting them.

We plan to recruit 50% of the total eligible stroke population at Charing Cross. Aiming for 24-38 patients to start the intervention, as advocated by feasibility literature (4). A 50% drop out rate is expected.

Participants who are subsequently discharged home will be able to continue in the study.

Frontline healthcare workers involved with patients that take part will be invited to take part in interviews and focus groups to discuss their feedback.

**Inclusion:** Adult stroke survivors (< 6 months) with arm impairment (including weakness, neglect, sensory deficits), who can:

- Provide informed consent
- Reliably communicate (this could be verbal or non-verbal)
- Read a short message (this is necessary as the intervention partly relies on the participants' ability to read short messages)

**Exclusion:** We are unable to recruit participants who at the time of recruitment are experiencing severe pain or oedema in the arm affected by their stroke. This is because their course of rehabilitation is different from a stroke survivor who isn't affected by these conditions, hence a comparison between samples would be impossible.

## **Dose**

Participants will be involved in the study for 14 weeks.

Participants will be loaned equipment needed for the study.

**Week 0:** Participants will wear activity trackers on both arms to gather a baseline of activity allowing left-to-right comparison and complete outcome measures.

**Weeks 1-12:** Participants will wear a smartwatch on their impaired arm only. They will receive real-time feedback on the amount of movement completed (measured in minutes) and daily motivational messages. Participants will receive regular consultations (approximately every two weeks) with an OnTrack researcher. During the consultation any problems will be addressed and feedback gained.

At the start of week 13 patients will be given two activity trackers to wear again for 1 week to reassess their amount of movement.

**Weeks 7 and 13:** Repeat outcome measures.

**Week 14:** Usability questionnaires and semi-structured interviews administered.

V 1.3 19-06-2019 IRAS Project ID 257058

Example messages include:

- “Hello, it’s the start of a new week, let’s continue to track your arm activity. If you haven’t already, put on the watch and press the blue START button to begin tracking. Are you ok to do this now?”
- “Hi, did you know about the Stroke Association? They have a wealth of resources for you, check them out by following this link”
- “Hello, let’s keep it simple during the weekend and stick to focusing on reaching your 60 minutes of activity”

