### **4.4 WITHDRAWAL CRITERIA**

- Participants are free to withdraw from the study at any time. However, anonymised activity data collected may still be used for data analysis as this is unlinked of any patient identifiable information.
- Participants will be withdrawn from the study if
  - they develop ongoing arm pain scoring 3/10 or more on the VAS or swelling in the affected arm during the study that is reported to be negatively impacted by wearing the tracker and taking part in the study.
  - Their treating therapist/medical professional is concerned about them participating.
  - Are not engaging with the process.

- They become unable to participate due to a change in their health or any other force majeure circumstances.
- If at any point the researchers become concerned about a participant's cognition or communication then the researchers will, in the first instance, discuss this with the participant's therapist, or if this is not possible, the participant will be withdrawn from the study.

Participants will be responsible for reporting a change in symptoms (pain, swelling, etc.) to researchers during the study.

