### 5. ASSESSMENT AND FOLLOW-UP

Participants will be involved in the study described above, their involvement lasting typically 14 weeks. No follow up after this point is planned.

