### 6. STATISTICS AND DATA ANALYSIS

#### Sample Size

24-38 patients.

Literature advocates a sample size of 12-30 participants at the completion of a feasibility study. A 50% drop out rate is expected. We have taken these two points into consideration in addition to what is realistic within our time frame/budget to come to our current sample size.

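### If the SUS is given only at week 14, criterion 3 would rest on at most about half of those who start and may overstate usability among starters

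*Combined protocol and SAP*

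**What the plan says.** Criterion 3 under Feasibility assessment criteria (Section 3) requires at least 80% "usability, measured by the System Usability Scale (SUS"). It gives no time point and no denominator.

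The schedule under Dose (Section 3) places outcome measures at weeks 0, 7 and 13. Week 14 has a line of its own: "Usability questionnaires and semi-structured interviews administered". No other visit names usability questionnaires. Section 5 then states: "No follow up after this point is planned".

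Two places point the other way:

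- The Study Summary lists the SUS among the outcome measures, and Dose repeats outcome measures at weeks 7 and 13.
- Analysis (Section 3) and Data Analysis (Section 6) say the process-evaluation data are meant to show change across the study, and the same sentence counts the SUS among those data.

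On numbers, Recruitment (Section 3) says "Aiming for 24-38 patients to start the intervention", and Sample Size (Section 6) says "A 50% drop out rate is expected".

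Section 4.4 lists the grounds for withdrawing a participant. One is "Are not engaging with the process". Another is ongoing arm pain or swelling that is "reported to be negatively impacted by wearing the tracker and taking part in the study". The rest are concern on the part of a treating professional, a change in health or other force majeure, and unresolved doubts about cognition or communication. For people who withdraw, the section says that "anonymised activity data collected may still be used for data analysis". It mentions no questionnaire at exit.

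**The concern.** Someone who finds the system hard to use may stop engaging, be withdrawn on that ground, and so never reach the visit at which usability is scored. The same can happen to someone whose arm is made worse by the tracker. The people who rate the system at week 14 would then be selected partly on the quality being rated.

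Criterion 3 is one of four numerical feasibility criteria and the only one measured by the SUS. Section 2 says the study will enable the design of a definitive trial, and Section 3 makes the later effectiveness study depend on the system proving feasible. The completion percentage and the adherence criterion would show how many people left, but not how those people rated the system. A pass on criterion 3 could therefore be read as a statement about everyone who started when it describes only those who stayed.

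**Working it through.** **Inputs.** 24-38 starters (Recruitment; Sample Size); 50% expected dropout (both places); 12-30 participants wanted at completion (Sample Size); 80% threshold (criterion 3). Everything else below is marked as assumed.

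**The plan's own figure.** Starters = completers / (1 - dropout).

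- Lower end: 12 / 0.5 = 24, as stated.
- Upper end: 30 / 0.5 = 60, not 38. Sample Size says time and budget also shaped the range, so 38 is not a pure formula result and is not called an error here.
- Forward check: 24 x 0.5 = 12 and 38 x 0.5 = 19, both inside the 12-30 target.

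**Number scored if the SUS is given at week 14 only.** At most about 12 of 24 or 19 of 38. This assumes that dropouts are not assessed at week 14 (dropout is not defined) and that every completer responds.

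**What a bare pass allows, share reading (assumed).** The criterion does not say whether 80% is a share of participants or a mean score. Take it first as a share. Bare pass = 0.8 x number scored, rounded up. The lowest share of starters counts every leaver as negative, and the highest counts every leaver as positive. The 40% and 30% dropout rates are assumed.

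| Dropout | Starters | Scored | Bare pass | Lowest | Highest |
|---|---|---|---|---|---|
| 50% | 24 | 12 | 10 | 10/24 = 41.7% | (10+12)/24 = 91.7% |
| 50% | 38 | 19 | 16 | 16/38 = 42.1% | (16+19)/38 = 92.1% |
| 40% | 24 | 14 | 12 | 12/24 = 50.0% | (12+10)/24 = 91.7% |
| 40% | 38 | 23 | 19 | 19/38 = 50.0% | (19+15)/38 = 89.5% |
| 30% | 24 | 17 | 14 | 14/24 = 58.3% | (14+7)/24 = 87.5% |
| 30% | 38 | 27 | 22 | 22/38 = 57.9% | (22+11)/38 = 86.8% |

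These are arithmetic limits of missing data, not estimates of bias. They lie on both sides of 80%.

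**Mean-score reading (assumed).** With half the starters scored and a completer mean of exactly 80, the mean over all starters is 0.5 x 80 + 0.5 x leavers' mean. Assumed leaver means of 50, 60, 70 and 80 give 65, 70, 75 and 80. If leavers score like completers, there is no bias.

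**What a week-7 SUS would add.** Suppose 25-75% of leavers go after week 7 (assumed). Then 12 x 0.25 to 12 x 0.75 = 3 to 9 leavers, or 19 x 0.25 to 19 x 0.75 = about 5 to 14, would have a score. Under the week-14-only reading none would. Exit scores would add to this.

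**The case against.** The strongest reply is that the plan may already intend a repeated SUS. The process-evaluation sentence in Analysis and Data Analysis, on data that show change over the study, includes the SUS, and the Study Summary places it among the outcome measures. This stands as a real ambiguity. It does not settle the matter: the sentence also covers interviews and usage data and gives no SUS dates, while the schedule separates usability questionnaires from the measures it repeats. If repetition is intended, the 12-19 figure no longer describes everyone with a score, but people leaving before week 7 would still have none.

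Second, stopping OnTrack need not mean losing the week-14 visit. Section 7.2 keeps participants in follow-up when a clinician gives alternative treatment. That clause is narrower than the withdrawals in Section 4.4, but it is one reason why 12-19 depends on an assumption.

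Third, leavers are not unheard. There are roughly fortnightly consultations, therapist check-ins, usage data and retained activity data. This stands, although none of these yields a SUS score.

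Fourth, rating usability after the full period of use is a defensible choice, and 12-19 completers meets the plan's own target. Both points are accepted; the concern is selection, not sample size.

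A reader might go further and infer that leavers' ratings cannot be obtained under this plan. The documents do not support that. An exit SUS is not forbidden, and Other (Section 3) allows measures to be added. The gap is that nothing ensures collection.

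**Conclusion.** The point holds as a conditional one. If the SUS is given at week 14 only, and dropouts are not assessed then, criterion 3 would be judged on at most about 12 of 24 to 19 of 38 starters. Two of the withdrawal grounds in Section 4.4 can plausibly be related to usability, so the score may overstate usability among starters. The remaining grounds need not be related to it.

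A reader might infer that the criterion is biased upward, or that a pass could conceal usability as low as 42%. Neither is shown. The documents give no scores for leavers and so establish neither the direction nor the size of any difference. The 42-92% range is only an arithmetic bound under an assumed share reading. Nor is week 14 only a stated rule; it is the more natural reading of the schedule. This is a worthwhile and inexpensive improvement to the design, not a defect that invalidates the study.

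**What to change.** 1. In Dose (Section 3), state when the SUS is given: at the existing week-7 assessment as well as at week 14. Offer an optional SUS at withdrawal with no reason required, in keeping with Section 7.2. If a repeated SUS is already intended, the week-7 part is only a clarification.
2. Keep the week-14 completer result as the main figure for criterion 3, and report respondents out of starters.
3. In Analysis (Section 3) and Data Analysis (Section 6), report leavers' week-7 and exit scores beside it, labelled by time. Add a sensitivity figure that uses each starter's last available SUS, and say how many starters have no score at all.
4. Call criterion 3 met without qualification only if the main and sensitivity figures agree. Without this step the extra scores would have no bearing on the conclusion.

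The withdrawal rules themselves need no change for this purpose.

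The cost is a protocol amendment and one short questionnaire at a contact that already exists and at exit, which adds a small burden for participants. Some leavers will decline, so their scores will stay incomplete. Week-7 and exit scores reflect shorter use and are not directly comparable with week 14, which is why the combined figure is a sensitivity analysis only. The usability result may also look less favourable.

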### **Therapist involvement**

Additionally, at the start of the participant’s involvement with the study, the therapists will provide information on their goals. Therapists will also have a ‘check-in’ call or email with researchers every 1-2 weeks to update the researchers on the participant’s progress. Additionally they will be invited to take part in an interview/focus group to discuss their experience of OnTrack.

### **Other frontline healthcare staff**

Will be invited to take part in interviews and or focus groups to discuss their experience of OnTrack.

### **Patients family/carer**

These individuals will be invited to share their thoughts and experiences of OnTrack with the researchers.

### **For all participants**

Sessions, interviews and focus groups may be audio recorded. Data will be anonymised as far as possible and sent to a transcription service. There may be instances where interviewees and/or session participants use someone’s name and this could be difficult to anonymise.

### **Analysis**

Analysis will be completed on the parameters and implementation of the study in addition to the usability of OnTrack.

Data collected for the process evaluation will capture changes over time and will be a combination of qualitative data from interviews with stroke participants, physiotherapists and frontline staff to explore their experiences of using OnTrack, as well as quantitative data on usage of OnTrack and the self-reported SUS. OnTrack therapy support sessions will be monitored through a fidelity checklist and observations. Interview data will undergo thematic analysis.

Data will be analysed for any association between the feasibility of the intervention and stroke subtype, patient demographics, stroke disability, and the amount of physiotherapy patients receive during the intervention period.

### **Other**

The list of outcome measures provided is not exhaustive and others may be used instead or in addition to the ones listed above.

Participants, with their consent, may be videoed or photographed at any point during the study. This data may be used for further development and/or dissemination (anonymised images/videos).

## **4. PARTICIPANT ENTRY**

### **4.1 PRE-REGISTRATION EVALUATIONS**

There will be no pre-registration evaluations necessary for eligible participants to be included in the study.

### **4.2 INCLUSION CRITERIA**

Adult stroke survivors with arm impairment (including weakness, neglect, sensory deficits), who can:

- Cognitively able to provide informed consent (advice will be gained from the patients therapy team if researchers are in any doubt)
- Reliably communicate (advice will be gained from the patients therapy team if researchers are in any doubt)
- Read a short message

Equipment will be loaned and previous smart-device experience isn't needed.

Therapists and other frontline healthcare staff involved with patients that take part will be invited to take part in interviews and focus groups to share their thoughts. Additionally, therapists will be asked to liaise with the researchers once every 1-2 weeks via phone or email to update researchers on the patients progress (anticipated phone call duration 5-15 minutes). They may also be asked to provide researchers with the results of any outcome measures that have been completed.

Patients carers/family members will be invited to share their thoughts.

